10.3 Planned Analyses

10.3.1 Primary Endpoint Analysis

The primary analysis will exclude patients who cancel (withdraw consent) prior to receiving treatment; we will tabulate the number (percent) of patients who withdraw prior to treatment and take actions if this percent appears to be greater than 5%. Patients who are randomized but received the opposite treatment to which they were randomized will be included in the analysis according to the treatment they received; it is expected

that the rate of patient crossover will be low. However, a sensitivity analysis using the fully intention to treat approach will also be performed. The primary endpoint will be analyzed using a one-sided log-rank test comparing the overall survival of the two arms and a one-sided (upper boundary) 95% confidence interval (CI) for the HR. If the 95% CI for the HR lies entirely below 1.6, this will be evidence that SBRT is non-inferior to SR. If the interval includes 1.6, this is evidence that SBRT is inferior to SR.

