4.1 Stratification Factors

The following stratification factors will be observed throughout the enrollment period of the study:

- Institutional intent to use brachytherapy: yes vs. no
- ECOG performance status (PS): 0 vs. 1 vs. 2

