10.2 Sample Size

This is a non-inferiority trial designed to determine whether the overall survival rate for SBRT is clinically (and statistically significantly) no worse than the overall survival for SR. We used published survival rates from the literature for SR in this patient population [2, 8, 19, 103]. The 3-year survival rate for SR (control group) appears to be approximately 80%. We will deem SBRT as non-inferior to SR if the 3 year overall survival rate for SBRT is no more than 0.10 less than that for SR. In other words, if the survival rate for SBRT at 3 years is more than 0.10 less than that for SR. In other words, if the survival rate for SBRT at 3 years is more than 0.10 less than the 3 year survival rate for SR, we will declare SBRT to be an inferior treatment compared to SR in terms of overall survival. To power the study, we assumed an exponential distribution for the survival rate and a HR of 1.60 (which reflects a 10% 3-year survival rate for SR is at least 0.10 greater than that for SBRT (0.80 for SR versus 0.70, or less, for SBRT). The alternative hypothesis is that the HR is 1.00 or that the 3 year survival rate for SR compared to SBRT is no more than 0.10. If we reject the null hypothesis, we will assume the two treatments are equivalent with respect to overall survival, if we do not reject the null hypothesis, we will assume that SR is superior to SBRT is no more than 0.10.

To determine the sample size for the trial we assumed a significance level of 0.05, an HR of 1.60 (SBRT versus SR, for the null hypothesis) and set power to be 90%. We plan a single interim analysis when half of the expected events (deaths) have occurred; this will be for futility only. Assuming a 3-year survival rate of 0.80, a HR of 1.60 yields a 3-year survival rate for SBRT of 0.70 or less for the null hypothesis. Assuming an accrual rate of 10 patients per month, an expected accrual duration of 40 months (3 1/3 years), and a minimum follow-up of 42 months (3.5 years), the necessary sample size is 400 eligible patients (200 per arm). To ensure that there is an adequate number of eligible patients (including patient refusals after randomization and prior to treatment), we will have a target accrual that is approximately 5% greater than this or 420 patients. This trial is expected to accrue in approximately 40 months and the final analysis will occur after 166 deaths have been observed or about 82 months (6.8 years) after the first patient is enrolled.

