In summary, a sample size of 200 eligible patients in each arm (target accrual is 420 including a 5% over accrual for patients who withdraw consent prior to treatment initiation) would mean that if the true hazard ratio is 1, then there is a 90% probability of declaring non-inferiority, and if the true hazard ratio is 1.6, there is a 5% probability of declaring non-inferiority.

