10.3.2 Interim Analysis

While this trial is accruing, we will be closely monitoring Z4032 for the maturation of its results. The results of this trial are expected to be mature in 12/2011. If the analysis of Z4032 indicates that either SR alone or SR with brachytherapy is superior to the other, we will amend this trial to use the therapy found to be superior in Z4032 as the treatment in Arm 1 (the SR arm) of this trial. At this point, we would also amend the sample size based on the results of Z4032, if needed.

A single formal interim analyses for futility based on the primary endpoint will be conducted after 79 deaths have been observed. The rationale for performing a single interim analysis for futility is based on the following considerations: (1) there may be different time-related patterns of treatment-related mortality in the two arms, i.e., the hazards may not be proportional; (2) stopping early for non-inferiority before all patient have been randomized may be inappropriate given the potential importance of the adverse event profile and quality of life endpoints in deciding the preferred treatment; and (3) as a non-inferiority trial, early stopping for "success" (i.e. non-inferiority) is not ethically necessary and may undermine the general acceptance of the result. The interim analysis will take place after half the expected trial information (i.e. 79 deaths) has been observed.

Assuming a baseline rate of a three-year survival of 80% for the SR, a sample size of 400 provides 90% power to declare non-inferiority if the three-year survival rates are truly the same (i.e. HR = 1), using a one-sided logrank test with alpha = 0.05 for falsely declaring non-inferiority when the true three-year survival rate for the SBRT arm is 70%. The calculations are based on a two-sample survival non-inferiority calculation, performed using EAST version 4.0, with an 80% 3-year survival for the control arm, and a 10% non-inferiority margin. A single interim analysis for futility for the primary endpoint will be conducted after 79 deaths have been observed, using an O'Brien-Fleming stopping boundary. The Z-scale boundaries are 0.031, for the interim analysis, and 1.63 for the final analysis; these correspond to a p-value of 0.49 and HR of 1.59 for the interim analyses boundaries and a p-value of 0.052 and HR of 1.23 to reject non-inferiority (the alternative hypothesis).

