10.3.3 Secondary Endpoint Analyses

Local-regional recurrence-free survival and disease-free survival will be compared using a one-sided logrank test. As for the primary analysis, we will exclude patients who are randomized but then cancel and refuse the treatment to which they were assigned. We will also perform the fully intention to treat approach as a sensitivity analysis.

Analysis of the adverse event rates and PFT values will involve chi-square tests and t-tests and Wilcoxon procedures at each time point as well as a repeated measures analysis of variance (ANOVA) and general estimation equations (GEE) modeling using data from all timepoints. [126] Models will include covariates of patient characteristics as well as treatment arm to perform a conditional analysis of treatment comparison in the presence of potentially confounding variables. The extent of missing data will be explored for non-random influences. [127] Sensitivity analysis will be performed using various simple imputation techniques to ensure results are not unduly influenced by the presence of missing data. [128,129] We examine the impact of imputing using such methods as last-value-carried forward, nearest-neighbor imputation, zero-value imputation, minimum-value imputation, and maximum-value imputation on the result original analysis. The degree of variability in the results will allow for a calibration of the impact of the best and worst case scenarios in terms of patterns in the missing data on the stability of the analytical results.

A tertiary analysis is planned that will compare the adverse events and PFTs profiles in each arm for patients with low or high Charlson Comorbidity Index scores, including a test interaction between Charlson Comorbidity Index scores (low vs. high) and treatment arm. Again, we will use appropriate modeling techniques. Modeling techniques will also be used to determine other prognostic variables that might be used to determine other characteristics that are associated with outcome in the different treatment arms.

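### Randomisation is stratified by performance status and brachytherapy intent, but the survival analyses name no strata and the pulmonary-function analysis names no baseline; the effect is small, but the estimand and the primary PFT model should be stated.

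*Combined protocol and SAP*

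**What the plan says.** Section 4.1 lists two stratification factors: "Institutional intent to use brachytherapy: yes vs. no" and "ECOG performance status (PS): 0 vs. 1 vs. 2". That makes 2 × 3 = 6 strata.

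Section 10.3.1 gives the primary analysis: "The primary endpoint will be analyzed using a one-sided log-rank test comparing the overall survival of the two arms", with a one-sided 95% upper confidence limit for the HR. The decision rule is: "If the 95% CI for the HR lies entirely below 1.6, this will be evidence that SBRT is non-inferior to SR". No strata, covariates or model for the HR are named. Section 14.1 refers to Cox analyses in the main body, but Section 10 specifies none. Section 10.3.3 gives one-sided log-rank tests for locoregional recurrence-free survival and disease-free survival, again without strata. Nothing in the plan expressly calls these tests unstratified; it is silent.

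For pulmonary function tests (PFTs), Section 10.3.3 says: "Analysis of the adverse event rates and PFT values will involve chi-square tests and t-tests and Wilcoxon procedures at each time point". The same sentence adds repeated-measures ANOVA and GEE over all timepoints, and the next one says that the models carry patient characteristics as covariates. Baseline PFT is not named among them, and no PFT analysis is designated primary. Baseline spirometry and DLCO are mandatory (Section 3, note 3), and Section 8.4 grades PFT toxicity against the patient's own baseline.

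**The concern.** An analysis normally reflects the factors used to balance the randomisation. Three things are at stake.

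- **Direction of bias.** Leaving a prognostic factor out of a proportional-hazards comparison pulls a non-null HR towards 1. Here the null is HR 1.6, so the pull is towards declaring non-inferiority, if the margin is meant within strata.
- **Balance.** The primary set in Section 10.3.1 drops patients who withdraw before treatment and analyses crossovers by treatment received. The balance secured at randomisation is therefore not guaranteed in the set analysed. Stratifying would protect against imbalance in these two factors; the direction of any imbalance is unknown.
- **Choice after the data.** Because the plan is silent on strata, on the HR model and on which PFT analysis leads, each can be settled after results are seen.

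For PFTs, a comparison of values at a visit that does not use a strongly correlated, universally available baseline gives up precision on a named secondary objective.

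**Working it through.** **Inputs from the plan.** One-sided alpha 0.05 (Section 10.3.2: "using a one-sided logrank test with alpha = 0.05 for falsely declaring non-inferiority"); 90% power at HR 1 (Section 10.2: "if the true hazard ratio is 1, then there is a 90% probability of declaring non-inferiority"); margin 1.6; 3-year survival 80% for SR and 70% at the margin; 400 eligible patients, 1:1; 40 months of accrual and 42 of minimum follow-up; 166 deaths at the final analysis (Section 10.2).

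**Reproducing the design.**
- Events (Schoenfeld) = 4(1.645 + 1.282)² / (ln 1.6)² = 155.1, rounded up to 156.
- Exponential survival with uniform accrual gives 154.6 expected deaths in 400 patients at HR 1.6. So 156 deaths need 400 × 156/154.6 ≈ 404 patients, against 400 stated.
- Power at 166 deaths = Φ(½√166 × ln 1.6 − 1.645) = Φ(1.38) = 91.7%. Section 10.3.2 treats 79 deaths as half, which implies 158; power is then 90.5%. The choice does not affect this point.

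**Scale of the margin.** ln 0.70 / ln 0.80 = 1.598. The 1.6 is thus derived from overall survival in each arm: a marginal HR.

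**Effect of omitting the strata.** The documents give no performance-status (PS) mix and no stratum hazards, so these are assumed: PS 0/1/2 = 25/55/20%; brachytherapy intent 40%. Each scenario used 12,000 simulated trials of 400 patients with 166 deaths, exponential hazards and allocation balanced within strata. Upper one-sided 95% Cox limits were compared with 1.6. The Monte Carlo standard error of a 5% rate is about 0.2 points.

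True within-stratum HR 1.6:

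| Strata (PS hazards; brachytherapy-intent HR) | Mean HR, unstratified / stratified | False non-inferiority, unstratified / stratified |
|---|---|---|
| Weak (1/1.25/1.6; 1.0) | 1.597 / 1.601 | 5.1% / 5.0% |
| Moderate (1/1.5/2.25; 1.2) | 1.590 / 1.606 | 5.1% / 4.7% |
| Strong (1/2/4; 1.5) | 1.553 / 1.600 | 6.1% / 5.0% |

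A smaller run (3,000 trials per setting, same PS mix, PS hazards 1/1.5/2.5 or 1/2/4) gave an unstratified HR of 1.58 or 1.56, and false non-inferiority of 6.0% or 6.1% unstratified against 5.5% or 4.5% stratified. Its standard error is about 0.4 points per rate.

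True HR 1: both estimates average 1.00. Power, unstratified to stratified, is 91.6% to 91.1% (weak), 91.5% to 90.8% (moderate) and 92.6% to 91.5% (strong).

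**The same question on the marginal scale.** Under the three scenarios, the within-stratum HR that yields exactly 80% versus 70% overall is 1.601, 1.607 and 1.628. At those values the unstratified test declares non-inferiority in 5.3%, 5.5% and 5.1% of trials, and the stratified test held at 1.6 in 5.2%, 5.1% and 4.0%.

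**PFTs.** With baseline–follow-up correlation rho, a baseline-adjusted visit comparison has variance (1 − rho²) times that of a plain t-test: 0.75 at 0.5, 0.51 at 0.7, 0.36 at 0.8 and 0.19 at 0.9. The correlations are assumed.

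**The case against.** The strongest objection is that the leniency depends on the estimand. The plan defines non-inferiority by an overall 3-year deficit of at most 10 points. Take PS alone with the assumed mix and hazards of 1/1.5/2.5 or 1/2/4, and a within-stratum HR of 1.6: SBRT survival is 70.1% or 70.3%, a deficit of 9.9 or 9.7 points. By the plan's own definition those are not false successes, and stratifying while holding 1.6 tightens the margin slightly. This stands. It is why the fix must state the scale as well as the strata.

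The size is also small, the stratum inputs are assumed, and stratifying costs a little power. All of that stands.

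A reader might infer that a log-rank test comparing the arms tests HR 1 and not the margin. The documents do not support this. Section 10.3.1 decides on the confidence limit against 1.6, and Section 10.3.2 sets alpha at 70% SBRT survival. The Section 10.3.2 boundaries also work only against the margin: 1.6 × exp(−0.031 × 2/√79) = 1.59 and 1.6 × exp(−1.63 × 2/√158) = 1.23, as printed.

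A reader might also infer that PFTs are compared only by unadjusted visit-wise tests. They are not: repeated-measures ANOVA and GEE with patient covariates are planned alongside. The variance ratios above apply against the t-tests, not against those models.

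**Conclusion.** The point holds in a modest form. The survival analyses name none of the randomisation factors, and the plan does not say whether the HR judged against 1.6 is marginal or within-stratum. On a within-stratum reading, the unstratified analysis is lenient by about 0.1 to 1.1 percentage points of false non-inferiority in the main simulation, and only strongly prognostic strata bring the rate to about 6%. On the marginal reading, from which the margin was derived, it is close to nominal at 5.1% to 5.5%. Stratified power stays at about 90% or more. These sizes rest on the assumed PS mix, brachytherapy-intent share and hazards.

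It would go too far to say that the plan chose an unstratified analysis or that its type I error is materially inflated; the first is silence, and the second depends on the estimand.

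For PFTs, the supportable point is that baseline PFT is not named as a covariate and no one analysis is primary. The precision at stake is real only if the unadjusted visit-wise tests are relied on.

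**What to change.** - **Primary endpoint.** Specify a log-rank test and a Cox HR with its one-sided 95% upper limit, both stratified by PS and brachytherapy intent and judged against 1.6. Add a pooling rule for sparse strata: under the assumed mix, PS 2 with brachytherapy intent would hold 0.20 × 0.40 × 400 = 32 patients.
- **Scale.** State whether the HR and the 1.6 margin are marginal or within-stratum, and keep them on the same scale. If the stratified HR is primary with 1.6 retained, say that this can be slightly stricter than the 80% versus 70% definition.
- **Sensitivity.** Report the unstratified HR as a pre-specified sensitivity analysis.
- **Other time-to-event endpoints.** Use stratified log-rank tests for locoregional recurrence-free and disease-free survival.
- **PFTs.** Make one repeated-measures model primary, with baseline PFT value, visit, arm, arm-by-visit and the two strata. Label the visit-wise t-tests and Wilcoxon tests as descriptive or supportive.

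The cost is wording in Section 10 and about 0.5 to 1.1 points of power. No patients, visits or data are added, because the strata and baseline PFTs are already collected.

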10.3.2 Interim Analysis

While this trial is accruing, we will be closely monitoring Z4032 for the maturation of its results. The results of this trial are expected to be mature in 12/2011. If the analysis of Z4032 indicates that either SR alone or SR with brachytherapy is superior to the other, we will amend this trial to use the therapy found to be superior in Z4032 as the treatment in Arm 1 (the SR arm) of this trial. At this point, we would also amend the sample size based on the results of Z4032, if needed.

A single formal interim analyses for futility based on the primary endpoint will be conducted after 79 deaths have been observed. The rationale for performing a single interim analysis for futility is based on the following considerations: (1) there may be different time-related patterns of treatment-related mortality in the two arms, i.e., the hazards may not be proportional; (2) stopping early for non-inferiority before all patient have been randomized may be inappropriate given the potential importance of the adverse event profile and quality of life endpoints in deciding the preferred treatment; and (3) as a non-inferiority trial, early stopping for "success" (i.e. non-inferiority) is not ethically necessary and may undermine the general acceptance of the result. The interim analysis will take place after half the expected trial information (i.e. 79 deaths) has been observed.

Assuming a baseline rate of a three-year survival of 80% for the SR, a sample size of 400 provides 90% power to declare non-inferiority if the three-year survival rates are truly the same (i.e. HR = 1), using a one-sided logrank test with alpha = 0.05 for falsely declaring non-inferiority when the true three-year survival rate for the SBRT arm is 70%. The calculations are based on a two-sample survival non-inferiority calculation, performed using EAST version 4.0, with an 80% 3-year survival for the control arm, and a 10% non-inferiority margin. A single interim analysis for futility for the primary endpoint will be conducted after 79 deaths have been observed, using an O'Brien-Fleming stopping boundary. The Z-scale boundaries are 0.031, for the interim analysis, and 1.63 for the final analysis; these correspond to a p-value of 0.49 and HR of 1.59 for the interim analyses boundaries and a p-value of 0.052 and HR of 1.23 to reject non-inferiority (the alternative hypothesis).

10.3.3 Secondary Endpoint Analyses

Local-regional recurrence-free survival and disease-free survival will be compared using a one-sided logrank test. As for the primary analysis, we will exclude patients who are randomized but then cancel and refuse the treatment to which they were assigned. We will also perform the fully intention to treat approach as a sensitivity analysis.

Analysis of the adverse event rates and PFT values will involve chi-square tests and t-tests and Wilcoxon procedures at each time point as well as a repeated measures analysis of variance (ANOVA) and general estimation equations (GEE) modeling using data from all timepoints. [126] Models will include covariates of patient characteristics as well as treatment arm to perform a conditional analysis of treatment comparison in the presence of potentially confounding variables. The extent of missing data will be explored for non-random influences. [127] Sensitivity analysis will be performed using various simple imputation techniques to ensure results are not unduly influenced by the presence of missing data. [128,129] We examine the impact of imputing using such methods as last-value-carried forward, nearest-neighbor imputation, zero-value imputation, minimum-value imputation, and maximum-value imputation on the result original analysis. The degree of variability in the results will allow for a calibration of the impact of the best and worst case scenarios in terms of patterns in the missing data on the stability of the analytical results.

A tertiary analysis is planned that will compare the adverse events and PFTs profiles in each arm for patients with low or high Charlson Comorbidity Index scores, including a test interaction between Charlson Comorbidity Index scores (low vs. high) and treatment arm. Again, we will use appropriate modeling techniques. Modeling techniques will also be used to determine other prognostic variables that might be used to determine other characteristics that are associated with outcome in the different treatment arms.
